Study Title: Pilot Study: Extended Regional Anesthesia to Prevent Chronic Pain After Ankle Fracture Surgery

Protocol date: 11/30/2018

NCT number: NCT02950558

Study Title: Pilot Study: Extended Regional Anesthesia to Prevent Chronic Pain After Ankle Fracture Surgery

Research Team:

Principal Investigator: [name]

Sponsor:

US Air Force 711th HPW (DOD)

- 1. Length of time for research**
 - a. data collection completion: 1 year 6 months
 - b. data analysis and report writing/publication: 6 months
- 2. Research Location(s):** University of Cincinnati Medical Center (UCMC), Holmes Hospital (UCMC), West Chester Hospital and UC Medical Science Building/CARE Crawley
- 3. Abstract/Brief Overview:**

Chronic pain affects over a third of adults in the United States. Trauma and surgery are common precipitating causes of some chronic pain conditions, and up to 81% of combat trauma survivors have chronic pain. For many patients current treatments are ineffective. Preclinical studies suggest that blocking peripheral nerve activity early after a precipitating injury, for 5 – 7 days, can prevent chronic pain development. This pilot study will test the hypothesis that prolonged regional peripheral nerve block will reduce development of chronic pain in patients undergoing surgery for ankle fracture. Regional nerve block using local anesthetics delivered by ambulatory pump is used in some types of surgeries but is not routine for ankle fracture patients in our hospitals. Patients will be randomized to standard care (single shot peripheral nerve block prior to surgery) or experimental (the same single shot nerve block, followed by continuous popliteal nerve block with ropivacaine starting just after surgery). The primary outcome will be scores on a validated ankle/foot pain questionnaire that includes questions on function. Subjects will be followed for one year. Secondary outcome will be postoperative opioid use.

- 4. Purpose of Study:** (including specific aims and hypothesis)

This is a pilot study that will begin to test the hypothesis that 5 day regional nerve block will reduce chronic pain after ankle fracture surgery. Specific Aims are:

1. Enroll subjects undergoing ankle fracture surgery and randomize to receive standard-of-care single shot nerve block or the same block plus 5 day regional nerve block. .
2. Follow-up subjects to obtain pain ratings related to the operated ankle, and screen for potential problems.

- 5. Background:**

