In the experimental group, in addition to the standard single shot nerve block, subjects will receive a catheter to deliver continuous 5 day popliteal sciatic nerve block using a disposable ambulatory pain pump. The catheter will be inserted starting just prior to surgery. This procedure is readily added on to the procedure for single injection, which involves ultrasound (and in some cases nerve stimulation) guidance for insertion of a needle near the sciatic nerve at the popliteal fossa. As part of standard care for administering a peripheral nerve block, sedatives are administered on as needed basis. Typically the patient will receive midazolam 1 mg every 5 minutes as needed. The catheter is inserted

just after the nerve block injection, during the same procedure and using the same needle placement. If there is a major vascular injury during the catheter placement (placement of the peripheral nerve catheter into the artery as confirmed by withdrawal of blood from the catheter itself), the catheter will be withdrawn and the subject will not receive a pump. An ambIT portable pump (as currently used in the participating hospitals after some other types of surgeries) will be attached to the catheter at the time the block is placed, and continuous block with 0.2% ropivacaine will begin immediately after surgery. The drug delivery rate will be 6 mL/hour. An 800 mL bag of medication will be provided to the subjects to allow medication for a 5 day period without requiring the subject to return to the clinic for refill. This drug delivery rate is on the lower end of the range commonly used in our hospitals for patients taking home pumps after other types of surgeries, which are usually started at 8 mL/hour with the option of patient controlled boluses. Previous clinical studies examined infusion rates of 6 to 14 mL/hour. The lower, fixed rate was chosen for this study to help avoid toxicity, since the duration of the pump is longer than commonly used at our hospitals. The goal based on preclinical studies is to block abnormal spontaneous activity from the sensory nerves, which requires a lower dose than complete sensory block. The selected infusion rate should also avoid motor block. The daily dose will be 384 mg; the FDA data sheet [19] indicates that a cumulative dose of up to 770 mg over 24 hours is well tolerated and studies indicate that the peak systemic levels during prolonged infusion occur after approximately 3 days[12].

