The treatment will be open label due to the impracticality of blinding the physician or patient to the presence of local anesthetic in the 5 – day pump and the ethical barriers to subjecting patients to implantation of a catheter and empty or saline pump with no benefit to them. Per standard of care, patients in both the

experimental and control groups will also have other oral pain medications prescribed for use as needed.

Additional data routinely obtained for clinical purposes will also be collected including demographic variables, opioid use in the PACU, pain medications prescribed at discharge, and type of ankle fracture. Standard database templates will be used to record information from the medical record where appropriate.

The patients randomized to the 5 day pump group will be undergoing an experimental procedure: ambulatory pumps for peripheral nerve block (including popliteal) are already successfully used in our clinics (with patients taking the pumps home and doing the removal of the catheter there) in the context other surgeries; but this is not routinely done for ankle fracture surgery nor for the indication of preventing development of chronic pain. In addition, normally the pumps are used for a shorter period of time.

The standard follow-up appointments with the orthopedic surgeons following ankle surgeries are at 10 - 14 days, 5 – 6 weeks, and 3 – 4 months. These visits will allow for monitoring of unexpected problems in patients receiving the pumps. In order to have consistent monitoring, a single orthopedic doctor will review the charts of all the enrolled patients in the experimental group on a regularly scheduled basis (at least monthly). As per our grant proposal patient charts will be reviewed for up to 3 months after use of the pumps. In addition, [name] will act as medical monitor for the study. He will review subject's research data and adverse events to ensure patient safety. The medical monitor will have the power to temporarily or permanently halt enrollment, if it is deemed that patient safety is compromised.

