 A single serious adverse event of LAST requiring rescue medication, cardiac resuscitation, or transfer to the ICU.

During the 5 day period of ambulatory pump use:

 A single serious adverse event of catheter site infection requiring hospital admission.

 A single serious adverse event of LAST requiring hospital admission.

During the entire study period:

 A single serious adverse event of any life-threatening adverse event deemed possibly related to the use of the ropivacaine pump.

 Two subjects receiving pumps experiencing moderate adverse events of tinnitus and/or metallic taste in the mouth.

11. Data Safety monitoring plan and/or DSMB:

As discussed in section 6, the medical monitor, [name], will review subject's research data and adverse events to ensure patient safety.”

12. Data Analysis:

The primary outcome measure is SEFAS scores at the indicated time points. A secondary outcome measure is use of opioids in the immediate postoperative period.

Each SEFAS response has 5 ordinal response choices scored 0 through 4, with the lowest score (0) representing the most severe disability and the highest total score being 48. If subjects omit a question the score will be re-normalized; however, the Redcap interface will be designed to try to obtain an answer for each question. The Mann-Whitney test will be used to examine differences in the SEFAS scores at each time point. For analysis of SEFAS scores, the pilot study sample size of 20 per group is sufficient for detecting a difference in scores between groups of 9 points with a power of 0.8 and $\alpha = 0.05$ (using the standard deviation obtained from SEFAS use in an ankle surgery study[35]); this score would represent moving up one rank in 3/4 of the questions which would be a functionally meaningful improvement given the 0 – 4 ordinal scale employed. . Patients who are withdrawn from the study due to failure of the initial nerve block (see above) will be considered as screening failures; no follow-up data or questionnaire scores will be obtained. We consider that such a failure is unlikely to have any relationship to the chronic pain outcome we are studying. The same approach will be taken for patients who decide to withdraw from the study, or are withdrawn by the attending surgeon or anesthesiologist, after randomization but before the single shot nerve block procedure.

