**E. Variables in the analysis data set with Definitions**

Description
Patient unique ID
Age at ankle surgery
Date of ankle surgery
Weight and height at time of surgery
Date of enrollment
Gender
Race
Ethnicity
Randomized to control or experimental group?
Ankle fracture: number of malleoli affected
Grade of injury (defined as :closed injury, or open injury with Gustilo Anderson classification grade 1, grade 2, grade 3a, grade 3b, grade 3cr)
Opioid medication use in PACU: time, agent, dose, and route for each administration
Times entered and discharged from PACU
PACU discharge status (home, rehab facility, hospital, AMA)
Verbal pain scores in PACU (0 – 10 scale) and times at which recorded
Surgical Hardware: number of plates implanted, length and number of screw holes of each.
Estimated blood loss during surgery
Pain medication prescription at discharge (drug, dose)
Start time of surgery
End time of surgery
SEFAS score (2 week, 3, 6, 12 month post surgery)
Subject-reported analgesic use (2 week, 3, 6, 12 month post surgery)
Dates of post-surgical follow-ups (FU)
Weight bearing recommendation at each FU (non, partial, full, other)
Weight bearing current status at each FU [full, assisted (cane, walker, boot), non (crutch)]
Pain status at each FU (none, mild, severe)
Pain medication prescriptions at each FU (drug, dose)
Wound healing status at each FU (dehiscence, cellulitis , deep infection, healing well, other)
Range of motion at each FU
Re-operation required?
Date of re-operation

Indication for re-operation (infection, non-union, hardware failure, hardware removal, other)
Chronic pain conditions diagnosed at one year FU.

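### The scheduled safety chart review ends 3 months after pump use, which does not match the last clinic visit, the study-long stopping criteria or the SAP's chart outcomes, and no scheduled search for later events is described

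*Protocol*

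**What the plan says.** Protocol section 6 puts the standard orthopedic visits at "10 - 14 days, 5 – 6 weeks, and 3 – 4 months" and gives them a safety role: "These visits will allow for monitoring of unexpected problems in patients receiving the pumps". For consistency, "a single orthopedic doctor will review the charts of all the enrolled patients in the experimental group on a regularly scheduled basis (at least monthly"). The next sentence sets the limit: "As per our grant proposal patient charts will be reviewed for up to 3 months after use of the pumps".

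Other parts of the plan bear on the same question:

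- **Length of follow-up.** Protocol section 3: "Subjects will be followed for one year".
- **Stopping criteria.** Protocol section 10 groups them by period. The last group is headed "During the entire study period". It holds two criteria: one life-threatening event possibly related to the pump, and two pump subjects with moderate tinnitus or metallic taste.
- **Other chart review.** Protocol section 7 plans chart review of the orthopedic appointments for chronic pain and unforeseen pump complications. SAP section C plans extraction from the same three visits. Neither gives a 3-month limit.
- **Open-ended safety functions.** The medical monitor reviews research data and adverse events (Protocol sections 6 and 11), and every adverse event is to be recorded (section 10). Neither has an end date.
- **Late contacts.** Protocol sections 6 and 7 describe the 6- and 12-month contacts as collecting SEFAS and medication use, by internet, mail or telephone.
- **SAP outcomes.** Section E lists whether re-operation was needed, its date, and "Indication for re-operation (infection, non-union, hardware failure, hardware removal, other"), together with chronic pain diagnosed at one year. Section G names the EPIC chart as a source. Table 3 reports re-operation with no time horizon. Table 2 reports any chronic pain diagnosis at 12 months.

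**The concern.** The protocol leans on a visit that its own dedicated review mostly does not reach. If the 3-month sentence governs all chart review, it conflicts with Protocol section 7 and SAP section C. If it governs only the orthopedic reviewer, the text does not say so.

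Three things are at stake.

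- **Late events.** Persistent nerve symptoms, late infection or further surgery first charted at or after the third visit may be found only if the subject or a treating physician happens to report them.
- **Interpretation of the primary outcome.** The SAP's primary comparison is SEFAS at 12 months. A re-operation after the last clinic visit could change that score without being captured, and the indications listed include non-union and hardware removal.
- **Comparability of the arms.** The dedicated monthly review covers only the experimental arm of an open-label trial. If events found that way feed the adverse event or re-operation tables, that arm has been searched harder than the control arm.

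**Working it through.** The plan gives no figure to reproduce. The check is date arithmetic, followed by a comparison of passages.

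**Inputs.** Pump duration is 5 days from surgery (Protocol section 6: "continuous 5 day popliteal sciatic nerve block using a disposable ambulatory pain pump"). Review runs up to 3 months after pump use, the third visit is at 3–4 months after surgery, and follow-up is 12 months. Month length *m* is my assumption: 28, 30 or 30.44 days.

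**Step 1: end of review against the third-visit window.**
Review end = 5 + 3*m*. Window = 3*m* to 4*m*. Share of window covered = 5/*m*.

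- *m* = 28: review ends day 89; window days 84–112; covered 5/28 = 18%; outside 82%.
- *m* = 30: review ends day 95; window days 90–120; covered 5/30 = 17%; outside 83%.
- *m* = 30.44: review ends day 96.3; window days 91.3–121.8; covered 5/30.44 = 16%; outside 84%.

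If the 3 months are counted from surgery, the review ends as the window opens and covers 0%. A pump removed early gives a result between these two cases.

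The 82–84% is a share of the calendar window. It equals the share of third visits only if visits are spread evenly across the month, which no document states.

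**Step 2: follow-up after the dedicated review ends.**
1 − (5 + 3*m*)/(12*m*) = 1 − 96.3/365.25 = 74% with *m* = 30.44, or about 8.8 months. Counted from surgery it is 1 − 3/12 = 75%, or 9 months.

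**Step 3: follow-up after the last described clinic visit.**
Give the plan full credit for the chart reviews in Protocol section 7 and SAP section C, so that the third visit is reviewed whenever it occurs. The remaining time is 12 − 4 = 8 months to 12 − 3 = 9 months. In that period the only scheduled contacts are the 6- and 12-month surveys.

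**Step 4: what could reveal a late event in those 8–9 months.**

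- *Surveys:* SEFAS and medication use. No question on surgery, new treatment or complications is described.
- *Clinic visits:* none listed after 3–4 months.
- *Chart review:* Protocol section 7 and SAP section C are tied to the orthopedic appointments. The SAP's one-year chronic pain variable implies a later look at the chart, but no one-year clinic visit or dated chart check is described.
- *Medical monitor and adverse event recording:* open-ended, but they act on what has been captured. The route of capture at this stage is not stated.

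**The case against.** The strongest counter-argument is that the 3-month sentence concerns one reviewer and is not the whole safety system. The medical monitor and adverse event recording have no end date. Protocol section 7 plans chart review specifically for unforeseen pump complications, and the SAP extracts data from the third visit. Treating physicians can see pump use in the Epic chart (Protocol section 13), and consent already gives access to records on complications and chronic pain diagnoses. A reader might infer from section 6 alone that late pump complications go unreviewed, or that the study-long stopping criteria have no source of information after 3 months. The documents do not support either reading.

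The stopping-criteria argument is also limited. Twelve months is an inference from one-year follow-up and is not written in the criteria. Tinnitus and metallic taste are listed in section 10 as signs of local anesthetic toxicity, so a chart review months after a 5-day infusion would add little for that criterion. Late infection, nerve symptoms or re-operation would meet the other only if life-threatening and possibly pump-related. Section 1 allows 18 months for data collection; less 12 months of follow-up, that leaves about 6 months of enrollment if both figures hold, so many late events would come too late to affect enrollment.

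Finally, the limit is attributed to a grant proposal that is not available here, and the safety review need not set the horizon for the SAP's re-operation data.

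What is left after these points is narrower but real. The cut-off disagrees with other passages, and none of the continuing functions comes with a schedule or method for finding events after the third visit.

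**Conclusion.** The concern holds as an inconsistency and an ascertainment gap. It does not show that late complications are excluded from review.

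The dedicated review closes before 82–84% of the third-visit window, or all of it if counted from surgery. This rests on a 5-day pump and months of 28 to 30.44 days. It describes the section 6 review only and does not mean that those visits go unexamined.

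After the third visit, 8–9 of the 12 months have no described scheduled method for detecting complications or re-operations. This rests on reading the 6- and 12-month contacts as limited to what the protocol says they collect. A survey form or grant document not seen here could narrow the gap.

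With 40 evaluable subjects planned, few such events may occur. This is an inexpensive improvement to make, not a defect that undermines the trial.

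**What to change.** 1. Reconcile Protocol section 6 with section 7, the study-long stopping criteria in section 10, and SAP sections C and E. Run the chart review until each subject's third visit has taken place, and state the method and end date of adverse event ascertainment.
2. Add one chart check at 12 months. It would also give the SAP's one-year chronic pain variable a dated source.
3. Add one question to the existing 6- and 12-month surveys: any further surgery or new treatment on this ankle or leg, with date and reason.
4. Apply items 1–3 identically in both arms, so that the Table 3 comparison does not depend on how hard each arm was searched.
5. Define the Table 3 re-operation row as re-operation by 12 months.

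The cost is protocol and SAP wording, one survey question, and one or two extra chart looks per subject by existing staff. The record access described in Protocol section 6 already covers complications and chronic pain diagnoses. No treatment rule changes.

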Subjects will be contacted at approximately 14 days and 3, and 6, and 12 months following the surgery to complete a pain questionnaire, the SEFAS (Self-Administered Foot and Ankle Questionnaire). The SEFAS is designed to evaluate disorders of the foot and ankle. It does not require physician input, and a study of its use after surgery found it to be a valid, reliable, and responsive patient-oriented outcome measure [23]. It consists of 12 questions focusing primarily on pain and its functional impact on daily life activities [24], meeting the new recommendations to use functional and patient centered outcomes in clinical research on pain [25]. Subjects will also be asked to provide information about their medication use including pain medications, at each of these time points. The consent form is structured to allow access to the medical records to obtain information about relevant clinical variables such as medications prescribed, complications, and diagnoses of chronic pain conditions.

The follow-up contacts to obtain questionnaire data will be made according to the subject's preferred contact method. Surveys will be available for subjects to complete on the internet, or via paper copy mailed to them or via telephone, as per their preference. For survey time points that coincide with the orthopedic

doctor's follow-up, [name], the orthopedic surgeon involved with the study, may administer the survey.

7. Research data collection/study procedures:

Encounters: Consent and randomization will occur before the ankle surgery. For subjects in the experimental group, the catheter will be inserted just before surgery in conjunction with the standard-of-care single shot popliteal nerve block procedure, and local anesthetic perfusion will begin immediately after the surgery. All subjects will be contacted via their preferred method of contact to complete the pain survey (SEFAS) at 2 weeks, 3 months, 6 months, and 1 year after the surgery. Information about current pain medication use will also be collected at each of these time points.

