Neither Medidata Rave® nor REDCap databases will contain subject names. The subject's enrollment into the study will be noted in the Epic chart, including a notation about whether or not they received the 5 day pumps, so that treating physicians will be aware of this history. Only authorized study personnel will have access to the rest of the data. In response to our query, the REDCap staff indicated that the REDCap system was not the best tool for conducting some of the types of analysis proposed (such as Mann-Whitney). A subset of the data (at least 20%) will be verified for accuracy by the study monitor. Files exported from Medidata Rave® that are generated for analysis of the de-identified data will be stored on the research server. This College of Medicine server is password protected so that only members of the Research Director's laboratory can have access, and the directory containing study data will be further restricted so only the researchers directly involved in the study have access. The server contents are automatically backed up several times per day and retained off-site for 30 days.

Once the study has been completed, the subject log will be destroyed and only the de-identified electronic data will be kept. Only study personnel will have access to the de-identified data except as required for regulatory oversight.

14. Study Population (Including age, number of individuals, inclusion/exclusion)

Sample Size - Up to 60 patients will be enrolled in this single site pilot study.

Inclusion criteria –

- Adult patients of either sex, age 18 to 65
- Referred for surgery for open reduction and internal fixation for ankle fracture

- Agreed to have a single shot local nerve blockade (routinely offered as part of the standard-of-care but declined by some patients)

Exclusion criteria:

- patients unable to give informed consent in English
- unable to complete surveys in English
- unable to understand instructions for using the pump in English
- unavailable for follow-up
- Scheduled to enter a rehabilitation facility after the surgery (due to difficulty in conducting the 5 days of safety monitoring phone calls)
- polytrauma, i.e. undergoing other surgeries or having other fractures related to the precipitating cause of the ankle fracture
- infection such as abcess or bacterial infection; mild colds or upper respiratory infections do not require exclusion.
- peripheral vascular disease
- diabetes
- undergoing chemotherapy

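### The unblinded study surgeon may administer the self-report SEFAS at coinciding clinic visits: an avoidable and unrecorded risk to the 14-day and 3-month scores

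*Protocol*

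**What the plan says.** Protocol section 6 presents the SEFAS as a patient questionnaire and states: "It does not require physician input". It offers internet, mailed paper and telephone completion, by patient preference. Section 7 adds that a research nurse contacts patients who do not use online entry and enters their answers. Section 6 then makes an exception, opening "For survey time points that coincide with the orthopedic" follow-up, under which "the orthopedic surgeon involved with the study, may administer the survey".

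The two schedules are also in section 6. For clinic: "The standard follow-up appointments with the orthopedic surgeons following ankle surgeries are at 10 - 14 days, 5 – 6 weeks, and 3 – 4 months". For the questionnaire: "Subjects will be contacted at approximately 14 days and 3, and 6, and 12 months following the surgery to complete a pain questionnaire".

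On blinding, section 6 says: "The treatment will be open label due to the impracticality of blinding the physician or patient". Section 13 has enrolment recorded in the chart, "including a notation about whether or not they received the 5 day pumps, so that treating physicians will be aware of this history".

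On the endpoint, Protocol section 12 says: "The primary outcome measure is SEFAS scores at the indicated time points". SAP section B makes the one-year score primary (Aim 1) and places the 14-day, 3-month and 6-month scores under Aim 2.

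Neither document describes a script for administering the SEFAS; the script mentioned in Protocol section 6 is for the daily safety calls. The SAP does not mention the surgeon's role. Its variable list (section E) has no item for mode of completion or for who assisted, and no analysis by mode is planned.

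**The concern.** In an open-label trial with a patient-reported outcome, the patient's own knowledge of treatment cannot be removed, and the Protocol explains why. A clinician who knows the allocation and takes the patient through the items is a second, separate influence, and the Protocol gives no reason for needing it. Such a clinician might prompt, explain or accept answers differently in the two arms. Section 6 gives one setting in which that could happen: it describes the clinic visits as a chance to watch for problems in patients who received pumps, so attention at those visits may not be the same in both arms. The influence could run in either direction.

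At stake are the early SEFAS comparisons and their use in planning a larger study. Because surgeon administration is optional and the plan provides no record of it, an imbalance between arms could be neither seen nor examined afterwards.

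**Working it through.** **Step 1. Which scores can be reached.** Set the two schedules in Protocol section 6 side by side.

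| SEFAS time point | Listed orthopedic visit | Coincides? | Role in SAP | In Protocol's primary wording? |
|---|---|---|---|---|
| 14 days | 10-14 days | yes | Aim 2 | yes |
| 3 months | 3-4 months | yes, in part | Aim 2 | yes |
| 6 months | none | no | Aim 2 | yes |
| 12 months | none | no | Aim 1, primary | yes |

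The 5-6 week visit matches no SEFAS time point. The exposure is therefore two of three Aim 2 tests, two of the four Protocol time points, and not the SAP primary.

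**Step 2. Whether the surgeon is blinded.** No. Section 6 leaves physicians unblinded, and section 13 puts pump receipt in the chart.

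**Step 3. Whether the route is needed.** Not for obtaining answers: section 6 says no physician is required and offers three other modes. It is, however, the only in-clinic capture that the Protocol describes.

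**Step 4. When it would distort the comparison.** Let f be the share of patients whose SEFAS the surgeon administers, taken as equal in both arms, and let s_E and s_C be the average shift in their scores in the experimental and control arms. The bias in the between-arm difference is f × (s_E − s_C). If s_E = s_C, it is zero. The documents give neither f nor the shifts.

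**Step 5. The SD.** Protocol section 12 states 20 per group, a 9-point difference, power 0.8 and alpha 0.05. It takes the SD from a cited study without giving its value, so the power figure cannot be reproduced independently. Solving for the SD that yields power 0.80 gives 10.16 (two-sided normal approximation) or 9.90 (two-sided t-test). The illustration assumes an SD near 10, with 8 to 12 as the range.

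**Step 6. Illustration only.** Assume no true effect and 20 per arm. Then SE = SD × √(2/20), and the two-sided rejection rate for a net shift b is Φ(−1.96 + b/SE) + Φ(−1.96 − b/SE).

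- SD 9.9: SE = 9.9 × 0.3162 = 3.13.
  - b = 1: b/SE = 0.32; rate = 0.050 + 0.011 = about 6.2%.
  - b = 2: b/SE = 0.64; rate = 0.093 + 0.005 = about 9.8%.
- SD 8: SE = 2.53; rates 6.8% and 12.4%.
- SD 12: SE = 3.79; rates 5.8% and 8.2%.

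A t-test calculation with SD 10 gives 6.1% and 9.5%. A net shift of 1 point would arise, for example, if f = 0.5 and s_E − s_C = 2; a net 2 points if f = 0.5 and s_E − s_C = 4. Two points is 2/9 = 22% of the 9-point target. These values of f and of the shifts are invented for scale.

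**The case against.** The strongest reply is that the sentence says little. To administer a survey may mean no more than handing over the form, and the SAP introduction uses the same verb for SEFAS collection at all four time points. The provision is optional and not tied to one arm. Both arms attend the same visits, so a general tendency to answer a surgeon more favorably would cancel. The questionnaire has fixed items and fixed response options, which limits room for prompting. Patients know their treatment anyway, and that is probably the larger source of bias. Research-nurse collection is not described as blinded either: the study nurse or another clinical team member makes daily calls about the pump, and nurse collection can reach the 12-month score. Finally, simply deleting the sentence would lose in-clinic capture in a pilot that hopes for 40 evaluable patients.

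Most of this stands, and it limits the point. It does not remove it: the wording also permits a surgeon-led interview, nothing prevents one, and nothing would record that it took place.

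Three stronger readings are tempting but unsupported:

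- **The interviewer is the patient's own operating surgeon.** Section 6 refers only to one orthopedic surgeon involved with the study. Section 15 has the surgeon scheduled for each operation asked for agreement to enrolment, which suggests several operators.
- **The 12-month primary is compromised.** No routine visit is listed after 3-4 months. SAP section E does list chronic pain diagnoses at a one-year follow-up, so a clinic contact at that time cannot be excluded entirely, but neither document schedules one.
- **The early comparisons are biased by 1 to 2 points.** That figure rests on assumed inputs.

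**Conclusion.** The point holds as an avoidable weakness of conduct, of low to moderate weight. The Protocol lets an unblinded physician administer an instrument that needs none, at visits coinciding with the 14-day and 3-month scores, with no SEFAS script described and no record of mode. Whether those scores count as primary depends on which document governs: they do under Protocol section 12 and do not under SAP section B.

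The documents do not show that bias will occur, and its size is unknown. The rise in the two-sided error rate from 5% to about 6-10% depends on a net 1 to 2 point shift that differs by arm, an SD near 10, 20 evaluable patients per arm and no true effect. With no arm-specific difference, the rate stays at 5%. The sample size is not affected.

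**What to change.** Replace the sentence in Protocol section 6 so that, at coinciding visits, the patient completes the paper or web SEFAS alone, without the surgeon asking the questions or seeing the answers. Where a patient needs help or chooses the telephone, have the existing staff read the items verbatim from a fixed script. The script should apply to the research nurse too, and at every time point. Add mode of completion and any assistance to the data collected with each SEFAS score and to the SAP variable list, so that the distribution by arm can be reported.

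The cost is small: a database field, a short script, and a form or link available in clinic. In-clinic capture is kept. The change does not address reporting bias from patients who know their own treatment, which should still be acknowledged when the results are interpreted.
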